1.2.3 Safety Considerations

Preclinical Safety of Recombinant Poxvirus-Based Vaccines

Preclinical immunotoxicology studies with pox-TRICOM vectors have previously been reported.((46)) CEA-Tg mice were injected with tumor cells that formed experimental metastasis. Fourteen days after tumor transplant, mice were vaccinated with rV-CEA-TRICOM s.c., followed by 3 weekly boosts of s.c. rF-CEA-TRICOM. Mice also received GM-CSF with the vaccinations and subsequent IL-2. Control mice with tumors were not vaccinated and died within 10 weeks. Immunotoxicology was performed at 1-year post-tumor transplant in mice cured of tumors, as well as in healthy age- and sex-matched controls. Parameters examined included: (a) In-Life Body weight, (b) Histopathology-50 Tissues per mouse, (c) Urinalysis-11 parameters, (d) serum chemistry-9 parameters, and (e) blood chemistry-7 panels. Neo-antibodies were studied specific for: B7.1, ICAM-1, LFA-3, GM-CSF, CEA, Vaccinia, and Fowlpox. Scl-70, ssDNA, dsDNA, Sm/nRNP, Histone, and CIC were studied for autoantibodies. No differences were found in any category between the treated group and the control group.((47)) Tissues

examined after treatment of CEA-Tg mice as outlined above showed no pathological effect coincident to the positive therapeutic effect of being cured of a CEA-positive tumor.

The Toxicology Branch of the NCI conducted a study of rV-PSA, replicating poxvirus, in rhesus macaques.((48)) The prostate gland of the rhesus is structurally and functionally similar to the human prostate; furthermore, there is 94% homology between the amino acid sequences of rhesus and human PSA. Three groups of four male rhesus monkeys were vaccinated by skin scarification once every 4 weeks for 3 vaccinations with nonrecombinant vaccinia virus (TBC-Wy) at 10^8 pfu/vaccination or with rV-PSA at 1×10^7 or 1×10^8 pfu/vaccination. Vaccination-associated clinical observations during the first 3 months of the study were limited to erythema at the vaccination site, regional lymphadenopathy, and low grade fever, which are typical symptoms following vaccinia inoculation. There was no evidence of any serious adverse effects. A complete necropsy with histopathology was performed on each animal. No treatment-related effects were noted in any of the parameters measured in this study.

Clinical Safety of Recombinant Poxvirus-Based Vaccines

Since 1991, 10 recombinant vaccinia-based vaccines and 8 recombinant fowlpox-based vaccines produced by Therion Biologics Corp. for the treatment of various cancers have been evaluated in human clinical trials sponsored by CTEP, DCTD, NCI. Over 700 cancer patients, most with metastatic disease, have been treated to date with these poxvirus-based vaccines in 29 CTEP sponsored or Therion Biologics Corporation sponsored clinical trials.(49) There have been no serious adverse events related to the vaccine when administered subcutaneously.(49) These trials represent a large component of the relevant safety database that supports the initiation of this proposed trial of rV- PSA(L155)/TRICOM and rF-PSA(L155)-TRICOM. Significant safety experience in humans includes: (a) vaccinia- and/or fowlpox-based vaccines safely administered by a variety of routes including intradermal (by injection or scarification), s.c., intramuscular, intravenous, and intratumoral at doses up to 2×10^9 pfu (vaccinia) or 6×10^9 pfu (fowlpox); (b) vaccinia-based and fowlpox-based vaccines containing costimulatory molecules, alone or in combination with CEA or PSA antigens, have been administered without serious adverse effects as outlined below.

Pox viral vectors containing PSA, either alone or with B-7.1 or TRICOM, have been evaluated in 9 different Phase I and II clinical studies comprising over 200 vaccinated patients with advanced prostate cancer. There have been no serious toxicities attributed to the vaccine.((17),(19),(20),(23),(44)) (clinical and immunologic data to these referenced trials are presented on pages 8-12)

A completed Phase I clinical trial at Georgetown University evaluated the safety of rV- and rF-CEA(6D)/TRICOM vectors.((50)) Fifty-nine patients were accrued, completing all 6 dose escalation cohorts as well as a seventh and eighth cohort with GM-CSF. Only mild treatment-related toxicity has been observed to date. Another trial at Fox Chase Cancer Center completed enrollment with 62 patients in a CEA(6D)/TRICOM based trial. A third trial at Duke University incorporates DC infected with rF-CEA(6D)/TRICOM, then given intravenously. This trial has enrolled 15 patients (as of 8-20-04). To date, we are unaware of any significant toxicity associated with these vectors, further supporting the safety profile seen in patients tested in the earlier pox viral studies.

1.2.4 Androgen Suppression and Immune Response

Since the seminal work of Huggins and Hodges in 1941 establishing androgen dependence of prostate cancer proliferation, androgen deprivation has served as the cornerstone in the management of metastatic prostate cancer ((51)). Androgen deprivation can be achieved surgically by orchiectomy, medically by a LHRH agonist such as leuprolide, or a combination of LHRH agonist plus an androgen receptor antagonist (ARA), e.g., bicalutamide for a CAB. Despite initial response rates of 80 to 90%, virtually all men progress to androgen insensitive disease. When antiandrogen withdrawal fails, one therapeutic option is the use of alternative ARA as second-line hormonal therapy ((52),(53)). The nonsteroidal antiandrogens approved by the FDA and commonly used in the United States are flutamide (Eulexin), bicalutamide (Casodex) and nilutamide (Nilandron). They bind to the AR and inhibit the stimulatory action of testosterone and dihydrotestosterone (DHT). DHT is the primary androgen that stimulates the growth of prostate tissue including prostate cancer. It is unclear why patients may respond to a second ARA agent after initial progression, but it is presumed that specific antiandrogens interact differently with the AR on prostate cancer cells ((54)).

Mercarder et al. demonstrated that androgen ablative therapy induces profuse T cell infiltration of benign glands and tumors in human prostates ((21)). This data is discussed in detail in section 1.2.1, page 10. The induction of T cell infiltration in prostate tissues treated with androgen ablation may have implications for the immunotherapeutic treatment of prostate cancer ((21)). To understand the T cell response to prostate cancer, Drake et al., demonstrated that tumorigenesis allows T cell recognition of the prostate gland--but this recognition is tolerogenic, resulting in abortive proliferation and ultimately in hyporesponsiveness at the systemic level (see section 1.2.1, p.10 for more detail discussion). Androgen ablation was able to mitigate this tolerance--allowing prostate-specific T cells to expand and develop effector function after vaccination. These results suggest that immunotherapy for prostate cancer may be most efficacious when administered after androgen ablation ((47)). In the NCI 00C-0137 study we examined this concept of combining androgen ablative therapy with immunotherapy ((20)). Men

with hormone refractory prostate cancer with no measurable disease on scans were randomized to receive a pox vector PSA vaccine vs. the androgen receptor antagonist nilutamide. The median time to treatment failure on nilutamide was 7.6 months, with 3 of these patients coming off study secondary to drug toxicity. However, 12 patients on the vaccine arm had nilutamide added at the time of PSA progression. The median time for treatment failure after the addition of nilutamide was 13.9 months, for a total of 25.9 months from initiation of vaccine therapy. This suggests that the addition of hormone therapy following initial vaccine therapy may lead to an improved clinical benefit compared with hormone therapy alone. ((20))

1.2.5 PSA Doubling Time (PSADT)

D'amico et al. have demonstrated that the change in the PSA level during the year before diagnosis has been suggested to be significantly associated with Prostate cancer specific mortality. Following radiation therapy, Prostate cancer specific death and all cause death following PSA failure were noted for patients with a short PSA DT (ie 12 months or less) ((60)). Lee et al. reviewed the medical records of 621 men with nonmetastatic prostate cancer treated with radiation therapy and hormone therapy between 1989 and 2003. Only hormone therapy duration ($p = 0.008$) and PSADT ≤ 8 months (<0.001) were significantly associated with time to true clinical failure. The estimated 5-year rate of any clinical failure was 9.4% for men with a PSADT >8 months and 60.4% for men with a PSA doubling time ≤ 8 months ($p < 0.001$) ((61)). Therefore, based on various reports using a PSADT of greater than 12 months or 8 months as a good prognostic indicator, we plan to stratify using greater than 10 months vs. 10 months or less to differentiate patients who are at a greater risk of disease progression in our proposed study.

1.2.6 Rationale for treating castrate-resistant, non-metastatic prostate cancer patients.

This study is based on a previous study employing an earlier version of a vector-based vaccine targeting PSA and the anti-androgen nilutamide. The results of that study suggested that the combination of anti-androgen and vaccine could improve time to progression and overall survival. ((64);(65)). This previous trial did not require patients to have been treated with a previous anti-androgen prior to enrollment. In addition, a similar proportion of the patients who had no previous anti-androgen had a sustained response as those who had progressed on anti-androgen ((64)). The premise that hormonal therapy will enhance immune response as previously outlined (Section 1.2.4) remains valid, regardless of whether patients have progressed on a previous anti-androgen or not.

Based on the original trial design in the previous trial, the estimated time to progression was 7.6 months ((64)). This includes both PSA progression and new metastatic lesions. Additionally, this included a proportion of patients who had not progressed on previous anti-androgens. Overall there is great variability reported in the literature for time to progression with D0.5 prostate cancer and there is no clear data on time to PSA-progression in this population (D0.5 Prostate Cancer). A large study followed over 3000 prostate cancer patients in the PSA era from Johns Hopkins. The data from 91 patients who eventually developed metastatic disease suggested that time from D0.5 disease to metastasis was only 8 months in patients treated with primarily with radical prostatectomy. ((66)). This is consistent with the previous study here that

demonstrated a median time to progression of 7.6 months, which included PSA progression. This time to progression (7.6 months) also served as the statistical basis for this study.

1.2.7 Rationale for treating patients previously treated with flutamide in the (neo)adjuvant setting.

Many patients have been previously treated with flutamide, but still should be considered for re-treatment with flutamide and thus should be considered for this protocol. Some patients may have been treated with this agent previously as part of a neoadjuvant or adjuvant hormonal treatment for patients undergoing primary radiation therapy. For some patients, flutamide is administered for up to 6-8 weeks in an effort to prevent a “flare” after initial GnRH agonist. Others may have discontinued flutamide as part of an intermittent treatment approach. From a clinical stand point, if the patient has not had a rising PSA on previous flutamide, they could be re-treated with this agent with reasonable expectation of response. ((67)) Therefore, eligible patients may have been treated with previous flutamide as long as the patient did not have a rising PSA while on flutamide. Patients will be required to be at least 1 year removed from previous flutamide exposure.

2 ELIGIBILITY ASSESSMENT AND ENROLLMENT

2.1 Eligibility Criteria

2.1.1 Inclusion Criteria

- A. Histopathological documentation of prostate cancer confirmed in the Laboratory of Pathology at the NIH Clinical Center or participating institute's Department of Pathology prior to starting this study. If no pathologic specimen is available, patients may enroll with a pathologist's report showing a histologic diagnosis of prostate cancer and a clinical course consistent with the disease.
- B. Must have non-metastatic androgen insensitive prostate cancer with a rising PSA with castrate levels of testosterone and no evidence of metastatic disease on CT scan or bone scan. A rising PSA is defined as two consecutively rising PSA levels, separated by at least 1 month apart, with the last measurement that is $> 1\text{ng/ml}$. Patients on nilutamide therapy must undergo nilutamide withdrawal for at least 4 weeks and still show evidence of a rising PSA. Following treatment with bicalutamide, patients must undergo withdrawal for at least 6 weeks and still show evidence of a rising PSA.
- C. Life expectancy greater than or equal to 6 months.
- D. ECOG performance status of 0-1.
- E. No systemic steroid or steroid eye drop use within 2 weeks prior to initiation of experimental therapy.
- F. Hematological eligibility parameters (See [APPENDIX C.](#))
 - Granulocyte count $\geq 1,500/\text{mm}^3$
 - Platelet count $\geq 100,000/\text{mm}^3$
 - Hgb $\geq 9\text{ Gm/dL}$
 - Lymphocyte count $\geq 500/\text{mm}^3$.
- G. Biochemical eligibility parameters (within 16 days of starting therapy)
 - Hepatic function: Bilirubin $\leq 1.5\text{ mg/dl}$, OR patients with Gilbert's syndrome, a total bilirubin $\leq 3.0\text{ mg/dL}$, AST and ALT < 2.5 times upper limit of normal
- H. No other active malignancies within the past 3 years (with the exception of non-melanoma skin cancers or carcinoma in situ of the bladder) or life threatening illnesses.
- I. Willing to travel to the NIH for follow-up visits.
- J. 18 years of age or greater.
- K. Able to understand and sign informed consent.
- L. Must agree to use effective birth control (such as a condom) or abstinence during and for a period of 4 months after the last vaccination therapy. Patients must be willing to remain on chemical castration therapy, unless they have had surgical castration.
- M. Patients must have recovered from acute toxicities related to prior therapy or surgery.
- N. Parameters for assessment of baseline renal function:
 - Serum creatinine ≤ 1.5 x upper limit of normal OR creatinine clearance on a 24-h

urine collection of ≥ 60 mL/min.

2.1.2 Exclusion Criteria

- A. Patients should have no evidence of being immunocompromised as listed below.
 - Human immunodeficiency virus positivity due to the potential for decreased tolerance and may be at risk for severe side effects
 - Concurrent use of topical steroids (including steroid eye drops) or systemic steroids. Nasal or inhaled steroid use is permitted
 - Patients who have undergone allogenic peripheral stem cell transplantation or solid organ transplantation requiring immunosuppression
- B. Patients who test positive for active Hepatitis B or Hepatitis C infection
- C. Patients should have no autoimmune diseases that have required treatment such as, Addison's disease, Hashimoto's thyroiditis, or systemic lupus erythematosus, Sjogren syndrome, scleroderma, myasthenia gravis, Goodpasture syndrome, active Grave's disease.
- D. History of allergy or untoward reaction to prior vaccination with vaccinia virus or to any component of the vaccinia vaccine regimen.
- E. Do not administer the recombinant vaccinia vaccine if the recipient, or for at least three weeks after vaccination, their close household contacts (close household contacts are those who share housing or have close physical contact) are: persons with active or a history of eczema or other eczematoid skin disorders; those with other acute, chronic or exfoliative skin conditions (e.g., atopic dermatitis, burns, impetigo, varicella zoster, severe acne, or other open rashes or wounds) until condition resolves; pregnant or nursing women; children 3 years of age and under; and immunodeficient or immunosuppressed persons (by disease or therapy), including HIV infection. See [APPENDIX B](#).
- F. Serious intercurrent medical illness (e.g., one that requires treatment) which would interfere with the ability of the patient to carry out the treatment program, including, but not limited to, inflammatory bowel disease, Crohn's disease, ulcerative colitis, or active diverticulitis.
- G. Patients with cardiac disease that have fatigue, palpitation, dyspnea or angina with ordinary physical activity (New York Heart Association class 2 or greater) are not eligible.
- H. Patients with a history of congestive heart failure or who have objective evidence of congestive heart failure by physical exam or imaging are not eligible.
- I. Patients with pulmonary disease that have fatigue or dyspnea with ordinary physical activity are not eligible.
- J. Concurrent chemotherapy.
- K. No known brain metastasis, or with a history of seizures, encephalitis, or multiple sclerosis.
- L. Patients with a serious hypersensitivity reaction to egg products are not eligible.
- M. Prior splenectomy.
- N. Patients who have received prior flutamide therapy in the last year. (Patients treated with flutamide in the neoadjuvant or adjuvant setting or those previously treated with flutamide who did not have a rising PSA on treatment would be allowed to enroll on the protocol.)

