2.3 Patient Registration and Treatment Randomization

All patients must have completed an eligibility checklist. Projected PSA doubling time is a stratification factor in the randomization (see formula in Section 5.4). Patients must be registered with Central Registration Information Services within 24 hours of signing the consent. Authorized staff must register patients by faxing the eligibility checklist from the web site (<http://home.ccr.cancer.gov/intra/eligibility/welcome.htm>) to the Central Registration Office at [contact].

For randomization, authorized staff should call [contact] between the hours of 8:30 a.m. and 5:00 p.m., Monday through Friday. A recorder is available during non-working hours.

For Participating site Registration:

All patients must be registered through the NCI Central Registration Office (CRO). The CRO is open from 8:30am to 5:30pm EST Monday through Friday, excluding federal holidays. A protocol registration form and cover memo will be supplied by the Coordinating Center, NCI CCR and updates will be provided as needed. Subject eligibility and demographic information is required for registration. To register a subject, fax the completed registration checklist and cover memo to the CRO at [contact]. Please indicate on the protocol registration form whether the patient is screening or is eligible to start treatment. The CRO will notify you either by e-mail or fax that the protocol registration form has been received. The CRO will assign a unique patient/subject ID number for each subject that will be used to enter data into the C3D data base. Questions about eligibility should be directed to the Coordinating Center's Research Nurse, [name], [contact], [contact]. Technical questions about the form should be directed to the Central Registration Office [contact]).

A copy of the registration checklist form should be faxed to Coordinating Center Research Team at [contact].

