3 STUDY IMPLEMENTATION

3.1 Study Design (see Schema)

This randomized Phase II study proposes to evaluate the role of second line antiandrogen therapy and a pox vector based PSA vaccine in a population of patients with prostate cancer who have a rising serum PSA despite castrate levels of testosterone and prior antiandrogen therapy but no metastatic disease on bone or CT scans. Patients will be randomized on a 1:1 basis to Arm A (flutamide alone) or Arm B (flutamide + vaccine).

Arm A: Flutamide 250 mg orally TID beginning on day 1.

Arm B: Flutamide 250 mg orally TID beginning on day 1.

PROSTVAC-V/TRICOM (vaccinia) 2×10^8 pfu subcutaneously on day 1 of the first cycle only, followed by monthly (every 4 week) boosting vaccinations with PROSTVAC-F/TRICOM (fowlpox) 1×10^9 pfu subcutaneously on day 1 of each cycle. The duration of each treatment cycle is approximately 28 days.

[figure not shown]
Patients may continue on the therapy they were randomized to until the development of measurable disease on scans, rising serum PSA, or if they develop toxicity requiring stopping of their treatment. For patients with declining PSA no restaging will be done unless they develop symptoms consistent with metastatic disease. For patients with rising PSA, once 2 consecutive

PSA rises are seen from the last imaging studies, CT and bone scans will be done at their next scheduled visit. They will then be re-staged (CT and bone scans) at 3 month intervals as long as PSA continues to rise.

1. Patients on either arm who develop clinical progression (i.e. evidence of metastatic disease on scans) will be taken off study.
2. Patients who do not develop clinical progression (as defined above), but develop biochemical recurrence (i.e rising serum PSA levels) will undergo the following:
 - After 3 months of therapy, patients randomized to the flutamide alone (arm A) may cross over to receive vaccine if they develop a rising PSA and scans are without metastatic disease. The vaccine may commence 4 weeks after flutamide is stopped (if the PSA continues to rise. If there is an antiandrogen withdrawal response (a decline in PSA 28 days after the discontinuation of flutamide), PSA serum levels will be checked every 28 days and vaccine may commence when the serum PSA levels begin to rise (if scans are negative for metastasis and if patients continue to meet the eligibility criteria as outlined in section 2.1).

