3.2 Drug Administration

Patients will receive vaccines at the NIH Clinical Center or other participating institution (see special handling procedures, section 8). Study drugs will be prepared and placed in syringes by the Clinical Center Pharmacy personnel at the NIH or Institution's Pharmacy Designates at the participating institution. Please section 3.1 for dose, schedule and route of administration.

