3.4 Protocol Evaluation: (See APPENDIX C)

3.4.1 All patients who are deemed eligible and who sign the informed consent form will be enrolled onto this trial.

3.4.2 A complete history and physical examination including ECOG performance status shall be done within 16 days of enrollment.

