15. Immediately report spills and accidents resulting in overt exposure to recombinant DNA molecules to the Institutional Biosafety Committee and NIH/OSP (Office of Science Policy). Send reports to the Office of Science Policy, National Institutes of Health, [name]. [contact]. Provide medical evaluation, surveillance, and treatment as appropriate and maintain written records of the event.

For more information about biohazard risk group classification and biohazard safety levels see:

- *NIH Guidelines for Research Involving Recombinant DNA Molecules (NIH Guidelines). See current version at: http://osp.od.nih.gov/sites/default/files/NIH_Guidelines.html*
- *Biosafety in Microbiological and Biomedical Laboratories; U. S. Department of Health and Human Services Centers for Disease Control and Prevention and National Institutes of Health. See current edition at: <http://www.cdc.gov/biosafety/publications/index.htm>*

Patient Care Implications and Contraindications

Cover vaccination sites with a sterile dry dressing (e.g., Telfa pad). Once the injection site is healed, no further barrier is necessary. As a precaution, protect injection sites that are exhibiting evidence of weeping, oozing or ulceration with a sterile dry dressing. In these circumstances, instruct patients to avoid direct contact of the injection site with susceptible individuals (e.g.; those who may be immunocompromised by disease or therapy). Instruct patients to avoid fathering a child for at least 4 months following therapy completion with the recombinant vaccine. Instruct patients receiving fowlpox vaccines to avoid direct contact with pet birds for at least 72 hours after vaccination or while there are any visible lesions at the injection site.

Due to the method of manufacturing (virus grown in primary chicken embryo dermal cells), patients with a history of allergy to eggs or egg products should not receive the vaccine.

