Due to the method of manufacturing (virus grown in primary chicken embryo dermal cells), do not administer the recombinant vaccinia vaccine to patients with a history of allergy to eggs or egg products. Do not administer the recombinant vaccinia vaccine to patients with a history of allergy or serious reaction to prior vaccinia vaccination (*e.g.*, smallpox vaccination).

Potential Complications Associated With Recombinant Vaccinia Vaccination

When vaccinia vaccine is administered by scarification for vaccination against smallpox, expected local reactions in individuals that have not previously been vaccinated with vaccinia include the appearance of a red papule in 3-4 days, followed by vesiculation in 5-6 days, and then the formation of a pustule on days 8-9. A large area of erythema may surround the vesicle and pustule. A crusted scab usually forms by the second week and sloughs by the third week, leaving a well-formed scar. Maximal viral shedding occurs from days 4-14, but can continue until the scab is shed from the skin. Other normal local reactions can include development of local satellite lesions, regional lymphadenopathy that can persist for weeks following healing of the skin lesion, considerable local edema, and intense inflammation from the vaccination (*i.e.*, viral cellulites), which may be confused with bacterial cellulites. Systemic symptoms typically occur between 8-10 days post-vaccination and include fever, malaise, headache, chills, nausea, myalgia, local lymphadenopathy, soreness and intense erythema surrounding the vaccination site.

When administered by scarification in individuals that have previously been vaccinated with

vaccinia, expected local reactions include the appearance of a clear cut pustule 6-8 days following vaccination or the development of an area of definite induration around a central lesion that may be an ulcer or scab 6-8 days following vaccination. The response to re-vaccination depends on the degree of residual immunity following previous vaccination. Similar systemic symptoms may occur, but typically at a lower frequency.

When recombinant vaccinia vaccines are administered by intradermal, intralesional, subcutaneous or intramuscular routes of injection, milder local reactions are expected, but similar systemic symptoms may occur.

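### Exclusion L bars only a serious egg reaction, but sections 8.1 and 8.2 bar both vaccine vectors for any history of egg allergy

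*Combined protocol and SAP*

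**What the plan says.** Three places in the protocol deal with egg allergy.

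- Section 2.1.2, item L (eligibility): "Patients with a serious hypersensitivity reaction to egg products are not eligible".
- Section 8.1, fowlpox boost, under patient care and contraindications: "patients with a history of allergy to eggs or egg products should not receive the vaccine".
- Section 8.2, vaccinia prime, under the corresponding heading: "do not administer the recombinant vaccinia vaccine to patients with a history of allergy to eggs or egg products".

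Sections 8.1 and 8.2 give the same reason, that the virus is grown in primary chicken embryo dermal cells. Neither limits the bar to serious reactions.

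One other exclusion might bear on the matter. Item D of section 2.1.2 excludes men with an allergy or untoward reaction to earlier vaccinia vaccination or "to any component of the vaccinia vaccine regimen".

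On entry, section 2.3 states "All patients must have completed an eligibility checklist", and section 3.4.1 states "All patients who are deemed eligible and who sign the informed consent form will be enrolled onto this trial". Section 3.1 randomises 1:1. It lets an Arm A man with a rising PSA and clear scans cross over to vaccine, in the withdrawal-response case "if patients continue to meet the eligibility criteria as outlined in section 2.1"; section 5.2.1 attaches the same condition to crossover.

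**The concern.** The entry rule and the dosing rule use different thresholds for the same hazard, and the entry rule is the looser one. Men with an egg allergy that never caused a serious reaction fall between the two: they may enter, but they may not be vaccinated.

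The stakes are mainly for the individual man. If staff apply section 8, a man assigned to flutamide plus vaccine receives flutamide alone, having been randomised to a treatment that was never open to him. If a site takes item L as the full rule on eggs, he receives a live recombinant virus, and then boosts every four weeks, against the product contraindication.

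There is a smaller analytic consequence. A man who could never receive the experimental treatment sits in the experimental arm and, being eligible as written, belongs to the population on which section 5.2.4.3 bases all conclusions.

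**Working it through.** The protocol states no figure on this point, so the check follows one hypothetical man through the text: he has a documented mild egg allergy and has never had a serious reaction.

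1. **Item L.** It requires a serious hypersensitivity reaction. He is not excluded.
2. **Item D.** It has no severity qualifier but does not name egg. Sections 8.1 and 8.2 give the formulation as phosphate-buffered saline with 10% glycerol, and egg is not listed. An investigator could read D either way, so it does not reliably exclude him.
3. **Rest of section 2.1.** No other criterion mentions egg.
4. **Enrolment and allocation.** Section 3.4.1 enrols all eligible, consenting men. Under 1:1 allocation his chance of Arm B is 1/2.
5. **If Arm B.** Section 8.2 bars the day 1 vaccinia prime and section 8.1 bars every fowlpox boost, so no part of the vaccine regimen can be given. Section 3.3 offers no vaccine dose modification. Section 5.4 counts rising PSA, metastatic disease or removal for excessive toxicity as treatment failure; withholding vaccine is none of these. He stays in follow-up on flutamide alone as an eligible Arm B patient.
6. **If Arm A.** A re-check at crossover uses section 2.1, which he still meets; section 8 then bars the vaccine. The rising PSA that opens crossover is itself a treatment failure under section 5.4, so his primary endpoint is already fixed and only the crossover analyses are touched.

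**Size.** After Amendment F the plan is 31 men per arm (section 5.4), so one such man is 1/31 = 3.2% of Arm B. The documents give no egg-allergy frequency. Purely for scale, suppose that between 0.1% and 1% of otherwise eligible men have a non-serious egg allergy. This range is an assumption with no support in the documents.

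- Expected number in Arm B: 31 × 0.001 = 0.03, up to 31 × 0.01 = 0.31.
- Chance of at least one: 1 − 0.999^31 = 0.03, up to 1 − 0.99^31 = 0.27.

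Even at the top of the range, the most likely number is zero (0.99^31 = 0.73). These figures cover the whole planned arm. A change to item L reaches only men not yet enrolled. Section 5.4 records 13 patients already enrolled by Amendment F, and the text now runs to Amendment P, so the number a change could still reach is smaller.

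**The case against.** The strongest reply is that the protocol already forbids dosing this man. Section 8 is part of the same document, and 8.2 is worded as an instruction not to administer. Vaccinating him would be a deviation. Section 8 also carries other dosing bars that 2.1.2 does not list, such as moderate or severe acute illness, so the eligibility list was never the only safeguard. Section 3.2 sends staff there ("see special handling procedures, section 8"). All of this stands, and a reader who inferred that the plan permits vaccination would be wrong. But section 8 acts at dosing, after randomisation. It can prevent the injection; it cannot prevent assigning him to an arm he cannot receive.

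A second reply is that item D may already cover egg, since both vectors are grown in chicken cells. It might be answered that L would then be redundant, but criteria in section 2.1 overlap elsewhere (steroid use and HIV each appear more than once), so redundancy does not settle it. What remains is that D does not name egg and L, which does, sets a higher threshold.

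Three stronger readings are tempting and not supported:

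- That he would pass the eligibility checklist. Section 2.3 requires one, but its content is not in the documents, and section 5.5 adds eligibility review at the coordinating centre.
- That L must be a slip because section 8 bars are otherwise carried whole into eligibility. They are not: 8.2 also calls for excluding clinically significant cardiomyopathy, which exclusion H does not name.
- That the primary comparison is materially weakened. Nothing in the documents shows this, and keeping a man despite a treatment deviation is already the approach of section 5.2.4.2 for response.

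**Conclusion.** The conflict is real and can be read directly from the text. As written, a man with a non-serious egg allergy is eligible under section 2.1 and may be randomised to vaccine, yet sections 8.1 and 8.2 bar him from both vectors. The conclusion rests on the wording of items D and L and the two contraindications; it does not depend on any prevalence.

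The practical size is small. The number of men cannot be estimated from the documents and may well be zero. No effect on power or on the trial's conclusions is claimed. The case for acting is that the inconsistency concerns participant safety and is nearly free to remove. The documents do not show which threshold was intended, only that the two disagree.

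**What to change.** Reword exclusion L to: *Patients with any history of allergy to eggs or egg products are not eligible.* Make sure the eligibility checklist uses the same wording. Leave sections 8.1 and 8.2 unchanged. Qualifying them to match L would also remove the conflict, but the documents give no basis for relaxing a product contraindication. Because section 2.1 is re-applied at crossover, the same edit covers Arm A men before vaccination.

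The cost is a one-line amendment, a checklist check, and possibly a very few extra exclusions. On the assumed 0.1% to 1%, that is 62 × 0.001 = 0.06 to 62 × 0.01 = 0.62 men over the full planned enrolment, and fewer among those still to enrol.
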